1.3. Schedule of Assessments

Day/Week	Open-Label Treatment				
	Visit 11	Visit 12	Visit 13	Telephone Call	Visit 14 or Early WD
Day/Week	Week 24 (Day 169) ^a	Week 28 (Day 197)	Week 36 (Day 253)	Week 44 (Day 308)	Week 52 or Early WD (Day 365)
Visit Window	±4 days	± 4 days	± 4 days	± 4 days	± 4 days
Informed Consent	X				
Subject Entry into IWRS	X				
Inclusion and Exclusion Criteria Review ^a	X				
AE/SAE Review	†	X	X	X	X
Concomitant Medication Review	†	X	X	X	X
IPSS ^b	†		X		X
[REDACTED]					
PGI ^b	†				X
[REDACTED]					
Vital Signs ^c	†	X	X		X
Brief Physical Examination	†				X
PVR volume	†	X	X		X
Laboratory Assessments ^d	†		X		X
Review and Data Enter Completed Bladder Diary ^e	†	X	X		X
Dispense Bladder Diary	X	X	X		
Dispense Open-label Study Drug	X	X	X		

AE = adverse event; [REDACTED] IPSS = International Prostate Symptom Score; IWRS = interactive web response system; OAB = overactive bladder; [REDACTED] PGI = Patient Global Impression; PRO = patient-reported outcomes; PVR = Post-void residual; SAE = serious adverse event; WD = withdrawal

- † For noted procedures, the Week 24 (Visit 11) assessments for Study URO-901-3005 serve as initial on-study visit for Study URO-901-3006; these procedures will not be duplicated.
- a Recheck clinical status before enrollment and first dose of open-label study drug. Initiation of Study URO-901-3006 should occur within 7 days of Study URO-901-3005 Week 24/End-of-Study visit.
- b PRO questionnaires should be completed prior to other procedures, including vital signs, blood draws, and study drug dosing.
- c Vital signs (including blood pressure [in triplicate], pulse, body temperature, respiration rate, and weight) should be taken prior to blood draws and study drug dosing.
- d Refer to Section 10.2 for a list of laboratory assessments performed.
- e Subject completes the Bladder Diary PRIOR to each visit.

2. Introduction

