1.1. Study Objectives and Endpoints

Assessments in Study URO-901-3006 are referenced to the initial Baseline (Visit 3) from Study URO-901-3005. Change from baseline (CFB) study endpoints for safety parameters for study URO-901-3006 are relative to the most recent assessment prior to starting vibegron. CFB study endpoints for efficacy in Study URO-901-3006 are relative to Study URO-901-3005 baseline. At the Week 52 visit, CFB comprises 52 weeks of vibegron exposure for subjects randomized to vibegron in Study URO-901-3005 and 28 weeks of vibegron exposure for subjects randomized to placebo.

With respect to study endpoints, “per day” refers to a “Diary Day”, which is defined as the time between when the subject gets up for the day each morning and the time the subject gets up for the day the next morning as recorded in the subject bladder diary (approximately a 24-hour period).

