3.1.2. Safety Analysis Set Extension

The Safety Analysis Set Extension (SAF-Ext) will serve as the primary population for the analysis of safety data in this trial.

The SAF-Ext consists of all randomized subjects in Study URO-901-3005 who

- a) have completed the 24-week treatment period in the Study URO-901-3005, and
- b) enrolled into the extension Study URO-901-3006 and received at least one dose of vibegron in this study.

Safety endpoints will be descriptively summarized for the entire Safety Analysis Set Extension. No imputation will be performed for missing safety data. Baseline will be established as the last observation prior to the first dose of vibegron. All safety data collected on or after the first exposure to vibegron within the combined experience of the patient on URO-901-3005 and

URO-901-3006 will be included in the safety analysis for URO-901-3006, and all analyses by visit will index visits from the first dose of vibegron on either study; subjects who received placebo in study URO-901-3005 will only contribute safety data up to Week 28.

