
First and last dose of vibegron refer to the first and last dose across both study URO-901-3005 and URO-901-3006, for subjects who were treated with at least one dose of vibegron in study URO-901-3006.
 
EOS: End of study is defined as the date when the subject has completed one of the following: completes Week 52 Safety Follow-up, discontinued from the study, or is lost to follow-up.
 
*AEs with a start date equal to the date of first dose of vibegron will be considered treatment-emergent unless the relatedness to study drug is marked ‘Not applicable’.
 
Overlapping period: Medication start date \leq period start date < medication end date, medication start date < period end date \leq medication end date, or period start date \leq medication start or end date < period end date, then the medication is considered overlapping with the period.
			

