2. For non-early withdrawal records, if a nominal visit number for a scheduled visit was assigned, then it will be used to summarize the record after checking to make sure that visit numbers match with therapy phases:

- Check that all records entered as a pre-treatment visit for study URO-901-3005 occur on or before the day of the first dose of double-blind treatment (i.e. day ≤1). Any record with day > 1 should be re-slotted to an on-treatment visit using the relative day window below.
- Check that all records slotted to an on-treatment visit for study URO-901-3005 and all records for study URO-901-3006 are on or after the day of the first dose of double-blind treatment. If they are not, the visit should be moved to pre-treatment.

3. Any early withdrawal record (regardless of the visit number assigned), any unscheduled visit record at any time, any repeat visit record, or any record for which the visit number was missing or the visit number was not for a scheduled visit, should be slotted or re-slotted to a visit using the window below.

Table 4: Analysis Visit Window Slotting

Analysis window label	URO-901-3005 Randomized Arm					
	Vibegron			Placebo		
	Nominal visit	Nominal day	Visit Window	Nominal visit	Nominal day	Visit Window
Baseline	Visit 3	1	NA ^a	Visit 3	1	[1,182 ^b]
Week 1	Visit 4	8	[2, 11]	NA	NA	NA
Week 2	Visit 5	15	[12, 22]	NA	NA	NA
Week 4	Visit 6	29	[23, 42]	Visit 12	197	[183 ^c ,224]
Week 8	Visit 7	57	[43, 70]	NA	NA	NA
Week 12	Visit 8	85	[71, 98]	Visit 13	253	[225,308]
Week 16	Visit 9	113	[99, 126]	NA	NA	NA
Week 20	Visit 10	141	[127, 154]	NA	NA	NA
Week 24	Visit 11	169	[155, 182 ^a]	NA	NA	NA
Week 28	Visit 12	197	[183 ^b , 224]	Visit 14	365	> Day 309
Week 36	Visit 13	253	[225, 308]	NA	NA	NA
Week 52	Visit 14	365	> Day 309	NA	NA	NA

a Must have occurred prior to the first dose administered in study URO-901-3005.

b Must have occurred prior to the date of first dose administered in study URO-901-3006.

c Must have occurred on or after the date of first dose administered in study URO-901-3006.

Note: The cut-off days to define the window for slotting through Week 20 are aligned with study URO-901-3005.

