For parameters which were **not** scheduled to be collected at all visits, the all-inclusive visit intervals defined for all visits (i.e., the window defined above) will still be used to slot records. If a value is slotted to a visit unscheduled for a parameter, it will not be summarized (and not be included in the efficacy datasets) but will be included in data listings.

4. If after all records have been slotted or re-slotted, there are multiple valid records within a visit, use the record following the rules below:
 - If there are multiple values for an endpoint in one window, the visit closest to the nominal day will be selected for by-visit displays. If the visits are equidistant from the nominal day, then the earlier visit will be selected. All values will be stored in analysis datasets.

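### For ex-placebo men who start the extension drug on the Week 24 visit date, SAP Table 4 drops the Week 24 safety values from baseline, contrary to SAP 1.1 and 3.1.2

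*SAP*

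**What the plan says.** SAP 1.1 measures safety changes "relative to the most recent assessment prior to starting vibegron". SAP 3.1.2 agrees: "Baseline will be established as the last observation prior to the first dose of vibegron". Both rules turn on the dose.

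SAP 4.2.4.2, Table 4, turns this into day windows. For men randomized to placebo in URO-901-3005 (ex-placebo men), the baseline window is Days 1 to 182, with footnote b: "Must have occurred prior to the date of first dose administered in study URO-901-3006". Their first on-vibegron window (Week 4, Visit 12) is Days 183 to 224, with footnote c: "Must have occurred on or after the date of first dose administered in study URO-901-3006". Footnote a to the same table, and footnotes b and d to Table 3, set their limits at the dose and do not mention its date.

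Table 2 (SAP 4.2.4.1) ends the Pre Treatment period before the date of first vibegron dose and begins Treatment on that date. Its note adds: "AEs with a start date equal to the date of first dose of vibegron will be considered treatment-emergent", unless relatedness is marked not applicable. SAP 7.3 counts an event as treatment-emergent only after the first dose.

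In the protocol (1.3 and 10.7.1), Visit 11 on Day 169 ± 4 holds the Week 24 assessments and the dispensing of open-label drug. Questionnaires come before dosing on a visit day, and vital signs "should be taken prior to blood draws and study drug dosing". Section 8.1 says the Week 24 assessments are not repeated on entry. Section 1.3 (note a) asks that the extension start within 7 days of the Week 24 visit.

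**The concern.** A man who is assessed and then takes his first extension tablet on the same day has his Week 24 values dated on the day of first dose. They were taken before vibegron and are the last such values he has. SAP 3.1.2 makes them his baseline; footnote b rejects them. Two programmers following different parts of the SAP would therefore produce different baselines for the primary (safety) objective.

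If Table 4 is followed, change from baseline for these men starts from an earlier placebo-phase visit, so any drift during the last weeks on placebo is carried into the change attributed to vibegron. A value measured on placebo might also be read as post-baseline in outputs that do not use visit windows.

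**Working it through.** The plan states no figure to reproduce. The check is on dates and on how the rules interact.

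1. **Day arithmetic.** Week 24 is 24 × 7 + 1 = Day 169 and Week 28 is 28 × 7 + 1 = Day 197. Their midpoint is (169 + 197)/2 = 183, which matches the 182/183 cut. With the ± 4 day window, Visit 11 falls on Days 165 to 173. The latest permitted first dose is Day 173 + 7 = 180, before Day 183.

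2. **All permitted combinations.** Nine visit days (165 to 173) times eight lags to first dose (0 to 7 days) give 72 combinations. This counts cases; it is not a probability.
   - Lag 1 to 7 days: 63 combinations. The Week 24 record meets footnote b and can be baseline.
   - Lag 0: 9 combinations. The record fails footnote b, and its day (at most 173) is below 183, so it is in neither the baseline nor the Week 4 window.
   - With dose-level wording, a pre-dose Week 24 record qualifies as baseline in all 72.

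3. **Does nominal-visit slotting rescue it?** Step 2 of the algorithm says that for records other than early withdrawal, "if a nominal visit number for a scheduled visit was assigned, then it will be used to summarize the record". Visit 11 is a scheduled visit, but the placebo columns of Table 4 have no row for it: the Week 24 row is marked not applicable and the nominal baseline visit is Visit 3. The step 2 phase check compares records only with the first double-blind dose, so it does not test the switch from placebo to vibegron.

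4. **Could footnote c pull the record into Week 4?** Only if it overrides the printed Day 183 edge. Even then the record lies 197 − 173 = 24 to 197 − 165 = 32 days from the nominal day, against 0 to 4 days for Visit 12. The tie rule is "If there are multiple values for an endpoint in one window, the visit closest to the nominal day will be selected for by-visit displays", so Visit 12 displaces it unless Visit 12 is missing.

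5. **What baseline becomes.** SAP 7.5 has vital signs at Week 20 (Day 141): 169 − 141 = 28 days older. SAP 6.1.2 and 7.8 have IPSS at Weeks 4, 8, 12 and 24, so the fallback is Week 12 (Day 85): 169 − 85 = 84 days older.

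6. **Outputs without visit windows.** SAP 7.4 and 7.5 use maximum and minimum post-baseline values (shift tables, eDISH plots, maximum vital-sign change) without defining post-baseline by date or by dose. Under Table 2 the same-day record is in the Treatment period, so it could be picked up. Under SAP 3.1.2 it would be the baseline and could not.

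7. **Size.** Assume half of 300 men are ex-placebo: 300 × 0.5 = 150. This fits the sample-size text, since 150 × (1 − 0.33) = 100.5, close to the 100 one-year completers expected. Same-day shares of 25%, 50% and 100% give about 38, 75 and 150 men. The documents give no share.

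   For vital signs, adding one on-placebo value to three scheduled on-drug values raises the expected maximum of independent standard normal values from 0.846 to 1.029, or 0.183 SD. With an assumed within-man SD of 9 to 11 mmHg for systolic pressure (not in the documents), that is 1.6 to 2.0 mmHg per affected man. Spread over all 300 men with 25% to 50% affected, it is about 0.4 to 1.0 mmHg. Laboratory tests have only two scheduled on-drug draws, so this figure does not carry over to them.

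8. **Adverse events (secondary).** Assuming 150 men, 25% to 100% dosed the same day, and 1% to 5% with an event dated that day but before dosing: 150 × 0.25 × 0.01 = 0.4 to 150 × 1 × 0.05 = 7.5 men, or 0.1% to 2.5% of 300.

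**The case against.** The best defence is that SAP 1.1 and 3.1.2 state the intended rule, and it is the right one. Table 4's footnotes look like a slip: in the vibegron columns the Week 24 window carries the footnote about preceding the first URO-901-3005 dose, and the Week 28 window carries the one about preceding the first URO-901-3006 dose. Neither can be meant. That argues against a deliberate difference between the arms, but not against correction. Table 4 is the only place where the ex-placebo safety baseline becomes a window.

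It is also fair that the windows are a fallback for scheduled records. As shown above, that route does not bring Visit 11 into baseline either.

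A reader might infer that Week 24 findings on placebo are generally moved to the vibegron side. The documents do not support that. The exclusion needs same-day dosing. By-visit values are left unassigned, and entry into maximum or minimum outputs is possible rather than prescribed. Protocol 8.3.4 also excludes men whose Week 24 laboratory abnormalities are judged clinically significant, which removes some of the values at issue.

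On adverse events, counting same-date onsets as treatment-emergent is a common conservative convention. It applies to both groups, turns on onset rather than detection, and has a not-applicable exception. What stands is only its mismatch with SAP 7.3.

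**Conclusion.** The point holds for ex-placebo men whose first extension dose falls on the date of the Week 24 visit. For them, Table 4 read literally gives a safety baseline that contradicts SAP 1.1 and 3.1.2, and it leaves the Week 24 values unassigned by visit. The fallback lags of 28 and 84 days follow from the documents. The number of men does not: it rests on the assumed equal split and an unknown same-day share, so it lies between none and about 150. The blood-pressure figure further assumes the SD and independent values, and it concerns one descriptive output with no testing.

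The premise that Week 24 values precede dosing is explicit for questionnaires and vital signs. For blood draws and post-void residual volume it is the natural reading, but it is not stated.

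This conflict sits beside a wider one: SAP 4.3.4 takes the safety baseline before the first double-blind dose, and Table 4 names Visit 3 as the nominal baseline for ex-placebo men. Settling that in favour of SAP 3.1.2 would not by itself cure the same-day exclusion in footnote b.

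**What to change.** Before database lock:

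- Reword Table 4 footnotes b and c by dose: prior to the first dose in URO-901-3006, and after it. Wording such as on or before the date would not do, because it would admit a same-day record taken after dosing.
- State that scheduled Visit 11 (Week 24) assessments are pre-dose and serve as the safety baseline for ex-placebo men. This also settles cases where no clock time was recorded.
- Make the Pre Treatment/Treatment boundary in Table 2 consistent for these assessments, so that they cannot count as post-baseline.
- Check the footnote markers on the vibegron-arm Week 24 and Week 28 windows in Table 4 at the same time, since footnote b is also attached to the latter.
- As a secondary matter, reconcile the same-date adverse event note in Table 2 with SAP 7.3 for events recorded at the Week 24 visit before dosing.

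The cost is SAP wording and programming. No data collection changes.

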10.7. Appendix 12: Study Schedule Supplement

10.7.1. Study Entry, Visit 11 (Week 24 [Day 169 ± 4 days])

- Obtain Informed Consent
- Assess inclusion/exclusion criteria
- Enter subject in IWRS
- Dispense open-label study drug

Note: The below (*) assessments performed at Week 24 of Study URO-901-3005 will be used for the initial procedures for Study URO-901-3006; they do not need to be repeated.

- * Review AEs/SAEs
- * Review concomitant medications
- * Administer IPSS, [REDACTED] PGI, [REDACTED] scales
- * Record blood pressure (3 results taken 1-2 minutes apart after sitting for 5 minutes), pulse, respiration, temperature, and weight
- * Perform brief physical examination
- * Measure post-void residual volume
- * Perform laboratory assessments
- * Review and data enter completed Bladder Diary

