Unscheduled visits will be assigned to a study visit using the all-inclusive windows defined in Section 4.2.4. However, data summaries for non-diary data will only report visits that are planned assessment time points for each parameter, according to the Time and Events table. All

visits for bladder diary data will be fully derived as described in section 4.2.4.2. Assessments at unscheduled visits will be included for “any time On-treatment” endpoints and in data listings.

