7.7. Post-Void Residual (PVR) Urine Volume

PVR urine volume data will be summarized at Baseline and every visit. The summary will comprise a continuous summary at each visit, including change from baseline, and a categorical summary of PVR at the following categories: <100 mL, ≥ 100 and < 200 mL, ≥ 200 and < 350 mL, and ≥ 350 mL. All PVR data will be listed.

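### SAP Table 4 gives ex-placebo men no analysis window from first vibegron dose through Day 182, so PVR values from withdrawals in that stretch enter no by-visit summary

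*SAP*

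**What the plan says.** **Timing of the first extension dose.** Protocol 10.7.1 places Visit 11 at Day 169 ± 4 and lists "Dispense open-label study drug" among its procedures. Footnote a of the Schedule of Assessments (Protocol 1.3) adds "Initiation of Study URO-901-3006 should occur within 7 days of Study URO-901-3005 Week 24/End-of-Study visit".

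**Windows for ex-placebo men.** In the placebo columns of SAP Table 4:
- Baseline is [1,182], with the footnote "Must have occurred prior to the date of first dose administered in study URO-901-3006".
- Weeks 1, 2 and 24 are not applicable.
- Week 4 (Visit 12) is [183,224], with the footnote "Must have occurred on or after the date of first dose administered in study URO-901-3006".
- Week 12 (Visit 13) is [225,308].
- Week 28 (Visit 14) is > Day 309.

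**Which records use the windows.** Scheduled records that are not early withdrawals keep their nominal visit (SAP 4.2.4.2, step 2). Step 3 sends the rest to the windows: "Any early withdrawal record (regardless of the visit number assigned), any unscheduled visit record at any time, any repeat visit record", and any record without a scheduled visit number.

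**What the SAP says of the windows.** SAP 4.2.2 states: "Unscheduled visits will be assigned to a study visit using the all-inclusive windows defined in Section 4.2.4". SAP 3.1.2 brings all safety data on or after first vibegron exposure into the analysis and counts by-visit analyses from first vibegron dose.

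**PVR reporting.** SAP 7.7: "PVR urine volume data will be summarized at Baseline and every visit". It specifies a continuous and a categorical summary, both by visit, and a listing.

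**The concern.** The two footnotes add a dosing condition to fixed day ranges. Neither moves the Day 182/183 cut to the date of dosing. A man who starts vibegron before Day 183 and has a withdrawal or unscheduled assessment by Day 182 is too late for Baseline, because he has been dosed. He is too early for Week 4, because Day 183 has not come. Nominal visit numbers do not help, since step 3 re-slots early-withdrawal records whatever number they carry.

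PVR is where this matters most. The protocol names urinary retention as a particular safety question in these men, its discontinuation criteria (7.1) include PVR, and PVR is part of the early-withdrawal visit. An ex-placebo man withdrawn for raised PVR in his first days on drug would have that value in no post-baseline row of the PVR table, including the higher categories. Those categories may be sparse, so one or two values could change what the table shows.

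**Working it through.** **1. Reproduce the plan's cut-offs.** The boundaries are midpoints of nominal days:
- (169 + 197)/2 = 183, so Baseline ends at Day 182 and Week 4 opens at Day 183.
- (197 + 253)/2 = 225, so Week 12 opens at Day 225.
- (253 + 365)/2 = 309, so Week 28 should open at Day 309. The table has > Day 309 after a window ending at Day 308, which leaves Day 309 unassigned. The same slip is in the vibegron columns of Table 4 and the non-diary columns of Table 3.

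**2. Range of first extension dose.** Earliest: 169 − 4 = Day 165. Latest: 169 + 4 + 7 = Day 180.

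**3. Days with no window.** For first dose on day *d*, the uncovered days are *d* to 182, that is 182 − *d* + 1.

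**4. Expected dropouts in the gap.** Inputs:
- about 300 men (SAP 1.2.4);
- an assumed equal split, giving 150 ex-placebo men. This fits the same section's 100 one-year completers after 33% dropout: 100/0.67 ≈ 149;
- 33% dropout, assumed evenly spread over 28 × 7 = 196 days.

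Expected dropouts = 150 × 0.33 × (gap days)/196.

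| First dose | Uncovered days | Expected dropouts, any cause |
|---|---|---|
| Day 165 | 18 | 4.5 |
| Day 169 | 14 | 3.5 |
| Day 173 | 10 | 2.5 |
| Day 180 | 3 | 0.8 |

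Each row assumes that every ex-placebo man starts on that day. At the nominal start the gap is 14/196 = 7% of the extension.

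**5. Which records can fall there.** The next scheduled clinic visit is Visit 12, at the earliest Day 197 − 4 = 193, and it keeps its nominal number in any case. Records after first dose and up to Day 182 are therefore withdrawal, unscheduled or repeat records.

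**6. Which summaries lose something.**
- *PVR*: scheduled at Visit 12, so it would be summarized at Week 4 if the window reached back. SAP 7.7 specifies nothing else that would catch it except the listing. Lost.
- *Vital signs*: also scheduled at Visit 12, so the by-visit row is lost. SAP 7.5 separately summarizes maximum post-baseline change and change to end of treatment.
- *Laboratory values*: not scheduled at Visit 12. SAP 4.2.2 and 4.2.4.2 leave a value slotted to a visit unscheduled for that parameter out of the summaries, so a longer Week 4 window would not recover it. SAP 7.4 has shifts to maximum, minimum and last post-baseline value.
- *Adverse events*: the treatment-emergent rule runs from first vibegron dose (SAP Table 2 and 7.3). Not affected.

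**The case against.** The strongest reply is that the intent is plain. The paired before-dose and on-or-after-dose footnotes, and the description of the windows as all-inclusive, suggest that the first-dose date was meant to be the cut. That is probably so, but the footnotes are worded as extra conditions on fixed days, and a programmer following the table would leave these records unassigned. If that was the intent, the change is a clarification.

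A reader might infer that ex-placebo men who withdraw early for safety reasons vanish from the safety report. The documents do not support that. A retention event soon after first dose still appears among the treatment-emergent events, the events of special interest and the events leading to discontinuation. The discontinuation reason is in disposition, and the PVR value is listed.

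A reader might also infer that the vibegron arm is fully covered over the same stretch of exposure. It has Week 1 and Week 2 windows, but SAP 7.5 makes Week 1 a telephone contact without vital signs. A vital-sign record slotted there is therefore also left out of the by-visit rows. Part of the loss is the SAP's general rule for off-schedule records.

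The objection to the count also stands. The 3.5 covers dropouts of any cause, and Protocol 7.2 requires withdrawal assessments only if possible.

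**Conclusion.** The gap is real on the text and contradicts the SAP's own rules, but its consequence is narrow. Through it, a few withdrawal or unscheduled values can be missing from the by-visit PVR table and, less importantly, from the by-visit vital-sign rows. On the even-dropout assumption the number of men is about 3.5 for a Day 169 start (0.8 to 4.5 across the permitted starts), and fewer of them will have a PVR record. The equal split and the timing of dropout are assumptions. The 7-day limit is worded as a recommendation, and SAP 9.3 says visit windows were widened by memo, so actual starts may fall outside Days 165 to 180. The study is descriptive, so no inference is at risk. The point is worth correcting because the affected values come from early withdrawals and unscheduled checks, and the correction is cheap.

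**What to change.** In the placebo columns of Table 4, make the first extension dose the boundary:
- **Baseline**: the last record before that dose, including a Week 24 record taken before dosing on the same date. This follows SAP 3.1.2; the current footnote, which works by date, would exclude such a record.
- **Week 4**: from the day after first extension dose (treatment day 2, already defined in SAP 4.3.3) to Day 224. Any record taken after dosing on the first-dose day stays in listings, and the footnote should say so.
- **No Week 1 or Week 2 rows** for these men. They have no scheduled visit there, so values slotted to those rows would still not be summarized.

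Change > Day 309 to ≥ Day 309 in Table 4 and in the non-diary columns of Table 3.

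With this boundary the uncovered stretch after the first-dose day is zero for every start from Day 165 to Day 180. The cost is a table edit and a derivation keyed to first extension dose. The downside is that a few values from early withdrawals enter the Week 4 row. Men who attend Visit 12 are still represented by the record closest to Day 197, under the existing rule for multiple records in a window.
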